5.6.3 Clinical Criteria for Early Trial Termination

Early trial termination will be the result of the criteria specified below:

- Quality or quantity of data recording is inaccurate or incomplete.
- Poor adherence to protocol and regulatory requirements.
- Incidence or severity of adverse drug reaction in this or other studies indicates a potential health hazard to subjects.
- Plans to modify or discontinue the development of the study drug.

In the event of Merck's decision to no longer supply study drug, ample notification will be provided so that appropriate adjustments to subject treatment can be made.

Specific details regarding the procedures to be followed due to subject discontinuation or withdrawal from the study are provided in Section 7.1.4 – Other Procedures – Withdrawal/Discontinuation.

The End of Treatment/ Follow-up visit procedures are listed in Section 6 (Trial Schedule of Events) and Section 7.1.5 (Visit Requirements). After the end of treatment, each subject will be followed for 30 days for adverse event monitoring (serious adverse events will be collected

for 90 days after the end of treatment as described in Section 7.2.5.3). Subjects who discontinue treatment for reasons other than progressive disease will have post-treatment follow-up for disease status until disease progression, initiating a non-study cancer treatment, withdrawing consent or becoming lost to follow-up.

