5.7 Treatment Beyond Disease Progression

Subjects may continue study treatment after standard RECIST v1.1 criteria for progressive disease are met provided they meet all the following criteria:

- Absence of symptoms and signs (including worsening of laboratory values, e.g., new or worsening hypercalcemia) indicating unequivocal progression of disease.
- Eastern Cooperative Oncology Group (ECOG) performance status 0 or 1.
- Absence of tumor progression at critical anatomical sites such as the central nervous system, central airway, the great vessels, and other organs or tissues where tumor progression would be expected to result acutely in severe and/or irreversible disability or death.
- Subjects must provide written consent to acknowledge discussion with the treating investigator of the benefit-risk balance of continuing study treatment beyond radiographic progression.
- If radiographic disease progression is confirmed at a subsequent tumor assessment, subjects may be considered for continued study treatment at the investigator's discretion after discussion with the Principal Investigator, if they continue to meet the criteria above and have evidence of clinical benefit, as evidenced by improvement in one or more symptoms or signs attributable to the underlying cancer.

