| Scheduling Window (Days): | -28 to -1 | | ± 3 | ± 3 | ± 3 | ± 3 | ± 3 | ± 3 | Within 30 days post treatment discontinuation | ±1 month |
| Tumor Imaging ^e (CT or MRI C/A/P +/- Whole Body Bone Scan ^d) | х | | | | X | | | х | | |
| RECIST 1.1 and irRECIST radiology read ^c | Х | | | | Х | | | Х | | |
| Archival Tumor Collection | Х | | | | | | | | | |
| Optional Fresh Tumor Biopsies (baseline and post-treatment) | Xe | | Xe | | | | | | | |
| • PD-L1 Testing | Х | | Х | | | | | | | |
| Immuno-Oncology Marker Testing | X | | X | | | | | | | |
| Correlative Studies | | | | | | | | | | |
| Bone Turnover Markers^g (in subjects with bone metastases only) | | Х | Х | | Х | | | X† | | |

^a Each treatment cycle = 3 weeks.

^b Urine pregnancy test is required only in women of childbearing potential.

^c CT or MRI CAP +/- bone scan and RECIST 1.1 assessments will be obtained at baseline and after every 3 cycles. irRECIST = immune-related response criteria. PET/CT is an acceptable alternative imaging modality. All scans can be performed \pm 7 days from the scheduled date.

d Whole Body Bone Scan is required for subjects with known or suspected bone metastases. All scans can be performed \pm 7 days from the scheduled date.

^e The baseline optional fresh tumor biopsy should be obtained during the screening period, prior to C1D1 treatment. The post-treatment optional fresh tumor biopsy should be obtained approximately 3-6 weeks (during cycle 2). Subjects may consent for separately for either baseline and/or post-treatment biopsies.

g Bone turnover markers may include β C-terminal telopeptide (β-CTX), bone specific alkaline phosphatase, and procollagen type 1 amino-terminal propeptide (P1NP). †Bone turnover markers will be collected through cycle 7 but not beyond. Bone tumor markers are not required during the second course of treatment.

ⁱ Total T3 = Total thriiodothyronine, Free T4= T4 (thyroxine) Free

^j Screening labs and pregnancy tests do not need to be repeated at C1D1 if done within 7 days of C1D1.

^k EKG tests will be performed through cycle 7, and then only as clinically indicated.

¹ In the absence of disease progression, pembrolizumab may be administered for up to 35 cycles (first course). If the patient progresses after discontinuing pembrolizumab, they may resume dosing for up to 17 additional cycles (second course), providing they meet criteria for retreatment. See protocol section 5.2.1 for additional information.

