8.2.3 Analysis of Anti-Tumor Activity

Descriptive statistics will be used to summarize all demographic and analytic data. Continuous data will be summarized using means, standard deviation, range, etc. Categorical data will be summarized using frequency tables.

Tumor response analyses will be based on definitions of responses according to both RECIST v1.1 and immune-related response criteria (irRECIST).

Objective response is defined as a complete or partial response, as determined by investigator assessment using RECIST and irRECIST. Subjects with missing or no response assessments will be classified as non-responders. For the primary objective, a one-sided exact binomial test will be used to assess whether the ORR is significantly greater than 20% in subjects taking a combination of pembrolizumab and cabozantinib.

Clinical benefit rate (CR + PR +SD) and duration will also be recorded.

Among subjects with an objective response, duration of response will be defined as the time from first occurrence of a documented objective response until the time of documented disease progression or death from any cause during the study, whichever occurs first. For all other subjects, duration of objective response will be censored at the day of the last tumor assessment.

Progression-free survival (PFS) will be defined as the time from study treatment initiation (Cycle 1, Day 1) to the first occurrence of documented disease progression or death from any cause during the study, whichever occurs first. For subjects who do not have documented progressive disease or death during the study, PFS will be censored at the day of the last tumor assessment.

Overall survival (OS) will be defined as the time from study treatment initiation (Cycle 1, Day 1) to death from any cause. For subjects who do not have documented death during or after the study, OS will be censored at the day of known survival status.

In subjects with bone metastases, time to progression of bone metastases or skeletal related event (SRE, defined as pathologic fracture, spinal cord compression, and radiation to bone or surgery to bone related to cancer) will also be recorded from Cycle 1 Day 1 to the time of progression or SRE.

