12.4.2 Post-Baseline Assessments Using irRECIST

Step 1. Identify the index target lesions.

Step 2. Add the sum of all target lesions. New lesions are incorporated in the total tumor burden measurement.

Step 3. Assess response per criteria in table below.

Step 4. Wait up to 12 weeks to confirm PD to account for flare.

Product: Pembrolizumab COMIRB 16-2300 Version Date: 6/17/2021 PI: [name]

| | Response Criterion |
|--|--|
| Immune-mediated complete response (irCR) | Complete disappearance of all lesions (whether measurable or not, and no new lesions). |
| Immune-mediated partial response (irPR) | Decrease in tumor burden \geq 30% relative to baseline. |
| Immune-mediated stable disease (irSD) | Criteria for irCR, irPR, and irPD are not met; does not require confirmation. |
| Immune-mediated progressive disease (irPD) | Increase in tumor burden $\geq 20\%$ relative to nadir (minimum 5 mm) confirmed by a consecutive assessment ≥ 12 weeks from the date first documented. |

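### Read literally, the irRECIST table scores a subject who progresses on a scan and then stops treatment as stable disease, because no later scan is planned to confirm the progression

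*Combined protocol and SAP*

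**What the plan says.** **Categories (section 12.4.2).** irPD needs an increase in tumour burden of at least 20% from nadir (minimum 5 mm), "confirmed by a consecutive assessment" at least 12 weeks after it was first documented. irSD is defined by exclusion: "Criteria for irCR, irPR, and irPD are not met; does not require confirmation". The table has no row for unconfirmed progression or for a subject who cannot be evaluated. Step 4 of the same section states the timing in the other direction: "Wait up to 12 weeks to confirm PD to account for flare".

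**Who continues after progression (section 5.7).** "Subjects may continue study treatment after standard RECIST v1.1 criteria for progressive disease are met provided they meet all the following criteria". The criteria include no symptoms or signs of unequivocal progression, ECOG 0 or 1, and no progression at a critical site. Section 5.6.2, by contrast, lists progression that has been confirmed on imaging as the reason for mandatory discontinuation.

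**Who is scanned after stopping (sections 5.6.3 and 6.0).** "Subjects who discontinue treatment for reasons other than progressive disease will have post-treatment follow-up for disease status until disease progression". The schedule's imaging row ("CT or MRI C/A/P +/- Whole Body Bone Scan") is marked at screening, cycle 4 and cycle 7, repeating thereafter, and is blank for the end-of-treatment and survival follow-up columns. On treatment, "RECIST 1.1 assessments will be obtained at baseline and after every 3 cycles".

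**Analysis (section 8.2.3).** "Tumor response analyses will be based on definitions of responses according to both RECIST v1.1 and immune-related response criteria (irRECIST"). Objective response is assessed by both sets. Clinical benefit is CR + PR + SD, with no minimum duration of SD and no criteria set named. Subjects with missing assessments are classed as non-responders.

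**The concern.** The irSD row takes in every case the other rows do not capture, and the irPD row asks for a scan that the plan does not schedule for one identifiable group: subjects whose scan meets the irRECIST progression threshold and who then stop treatment because of it. The rule places them in a favourable category by default.

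The missing-assessment rule in 8.2.3 does not correct this. It settles who is a responder, and an irSD subject is already a non-responder; it does not take anyone out of SD.

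What is at stake is the irRECIST response summary, a named secondary endpoint, and the clinical benefit rate and its duration if these are reported by irRECIST. The error runs in one direction, towards a more favourable result. With no written rule, the category would be chosen after the data are seen, in an open-label trial with investigator-assessed response.

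**Working it through.** The plan states no figure for irSD or for clinical benefit, so there is nothing to reproduce. The check is a trace of the rules followed by simple arithmetic.

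**1. Following one subject through the rules.** Take a subject whose first post-baseline scan shows an irRECIST increase of at least 20% from nadir (at least 5 mm) and RECIST 1.1 progression, with new symptoms of progression.
- Section 5.7: not all criteria are met, so treatment beyond RECIST progression is not available.
- Section 5.6.3: the reason for stopping is progressive disease, so the promised follow-up for disease status does not apply.
- Section 6.0: no imaging is planned at end of treatment or in survival follow-up.
- Section 12.4.2: irCR no, irPR no, irPD no (not confirmed). The category left is irSD.
- Section 8.2.3: SD counts towards CR + PR + SD if irRECIST categories are used. Under RECIST 1.1 the same subject is PD.

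**2. Whether a different confirmation interval would cure it.** For subjects who stop, it would not: no second scan is planned at any interval. For subjects who continue, there is a separate timing problem. Scans are 3 cycles × 3 weeks = 9 weeks apart. With a ±7-day window the next scan falls 8 to 10 weeks after an on-time scan, or 7 to 11 weeks after if both scans shift. The next scheduled scan therefore does not reach the 12 weeks in the irPD row; the first that does is the second one, at about 18 weeks.

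**3. Size per subject.** Effect on an irRECIST clinical benefit rate = 1/n.
- Full phase II, n = 38 (section 8.2.5): 1/38 = 2.6 points.
- Stage 1, n = 20: 1/20 = 5 points.

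This applies to a subject with no earlier scan showing SD or better. Because SD has no minimum duration, a later progressor already counts in the rate; for that subject the default affects duration.

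**4. Illustrative totals.** The documents give no rate for such subjects. Assume k of 38, with every other subject CR, PR or SD. The rate with those k counted as progressors is (38 − k)/38; the table read literally gives 38/38 = 100% each time.

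| Assumed share | k | Rate if scored as progression | Difference from 100% |
|---|---|---|---|
| 5% | 2 | 36/38 = 94.7% | 5.3 points |
| 10% | 4 | 34/38 = 89.5% | 10.5 points |
| 20% | 8 | 30/38 = 78.9% | 21.1 points |

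The difference is k/38 whatever the remaining subjects' results.

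**5. Primary endpoint.** ORR counts CR and PR only. Moving a subject between irSD and irPD changes neither, so the Simon two-stage decision is untouched.

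**The case against.** Several arguments limit the point.

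- **A second scan may exist.** Section 7.1 allows unscheduled procedures, section 5.6.2 speaks of confirmed progression, and Step 4 of 12.4.2 tells sites to wait for confirmation. A reader might infer that irPD can never be confirmed in these subjects. The documents do not support that; they support only that no planned scan would confirm it. Sections 5.6.2 and 5.7 also pull in different directions on whether stopping requires confirmation.
- **Clinical benefit may be a RECIST 1.1 measure.** The objectives list irRECIST response separately from clinical benefit, and 8.2.3 names both criteria sets for objective response but neither for clinical benefit. If RECIST 1.1 is meant, the benefit rate is not biased. The irRECIST response summary still is.
- **Not all rapid progressors are affected.** A subject who dies or deteriorates before any post-baseline scan has no assessment for the table to score. Nor is every RECIST progressor misclassified: irRECIST adds new lesions to total burden, so a small new lesion with less than a 20% increase in burden is properly irSD.
- **A larger figure is tempting.** Section 4.2.2.2 reports 28% PR and 52% SD in an earlier phase 1 cabozantinib study in RCC. A reader might treat the other 20% as progressors and infer a benefit rate inflated from 80% to between 90% and 100%. The protocol does not say that those 20% progressed, met the irRECIST threshold, or stopped without another scan, and the study was of cabozantinib at 140 mg/day, not the combination.
- **A fit-versus-unfit contrast.** It is tempting to say that progressors who continue treatment are readily confirmed as irPD. Under the table's 12-week minimum, their next scheduled scan does not qualify either.
- **The cited guideline may cover it.** Section 12.4 cites a published source, and its handling of unconfirmed progression cannot be checked from these documents. The protocol's own table does not address it.

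These arguments narrow the point but leave the gap: the written table gives the wrong category, and no written rule corrects it.

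**Conclusion.** The point holds in limited form. For a subject who meets the irRECIST progression threshold on a scan, stops for progression and has no further scan, the table in 12.4.2 read literally returns irSD. This affects the irRECIST response summary. It affects clinical benefit and its duration only if these are reported by irRECIST, which the plan does not say.

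The per-subject size, 2.6 points with 38 subjects or 5 points with 20, is arithmetic. Any total is an assumption, because the number of such subjects is not given. It rests on the table being applied as written, on no unscheduled scan being done, and on the subject having no earlier scan of SD or better.

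The primary ORR, the Simon decision and the RECIST 1.1 endpoints are unaffected. Clinical benefit is descriptive, with no test attached. It should be corrected before analysis, but it does not threaten the trial's main conclusion.

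**What to change.** - **Scoring rule, in 12.4.2 and 8.2.3:** a subject who meets the irRECIST progression threshold and has no later tumour assessment is scored irPD at the date of that scan, is not scored irSD, does not count as clinical benefit on the strength of that scan, and stays in the denominator.
- **Clinical benefit, in 8.2.3:** state whether CR + PR + SD is by RECIST 1.1, irRECIST, or each separately.
- **Confirmation interval, in 12.4.2:** reconcile the 12-week maximum in Step 4 with the 12-week minimum in the irPD row, and both with scans every 9 weeks.
- **Stopping wording:** sections 5.6.2 and 5.7 must be reconciled on whether stopping requires confirmed progression. Which reading is right is a clinical decision for the sponsor-investigator.

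**Cost:** the scoring rule is a text change only, with no extra scans or subjects. Its downside is that a few subjects with pseudo-progression who stop early will be scored as progressors, so the irRECIST benefit rate will be slightly less favourable.
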